CLINICAL USE OF A NEONATAL MRI SYSTEM

NCT03476343

January 9, 2020

CLINICAL USE OF A NEONATAL MRI SYSTEM

Date of initial IRB approval: February 11, 2018

Version: January 9, 2020

Principal Investigator:

[name]

Cincinnati Children's Hospital Medical Center

Study Location: Cincinnati Children's Hospital Medical Center (CCHMC)

Neonatal Intensive Care Unit (NICU)

ABSTRACT:

There are significant safety and image quality issues associated with transferring neonates from the Neonatal Intensive Care Unit (NICU) to the main Radiology Department for imaging in an adult-sized magnetic resonance imaging (MRI) scanner. For these reasons, the smallest and/or sickest neonates are typically precluded from receiving an MRI exam. The goal of our research effort is to bring high-performance MRI into the NICU so that all neonates can benefit from the same quality of diagnostic imaging as adults. To accomplish this, we have converted a commercial small-bore 1.5 Tesla (T) MRI scanner designed for orthopedic use into a neonatal MRI system optimized for whole body imaging of neonates (NICU MRI). To expand the imaging capabilities of the NICU MRI system, the measurement control electronics and operating system software of the FDA cleared OPTIMA platform have been augmented with state of the art HDX electronics and software currently used on a conventional commercially available adult sized whole body MRI scanner. The clinical safety of the integrated HDX/OPTIMA NICU MRI system and its ability to produce diagnostic image quality has been shown in 15 pilot patients (CCHMC Protocol 2011-2045). Further we have scanned almost 600 patients under a prior protocol (CCHMC Protocol 2011-2850) without an adverse event.

The present protocol seeks to allow continued performance of clinical MRI exams on the NICU magnet with improved administrative processes and procedures. NICU patients for whom an MRI exam is medically indicated will be recruited for the present study. Images will be obtained using both the FDA cleared OPTIMA NICU MRI platform and the integrated HDX/OPTIMA NICU MRI platform with the additional HDX images augmenting the OPTIMA images and contributing to diagnosis and guidance of subsequent clinical management. The specific MR imaging methods/procedures utilized will be determined by the type of exam to be performed and the medical indication. All of the MR images obtained will be reviewed by a board certified pediatric radiologist as part of clinical care and a clinical report will be generated and included in the infant's medical record.

PURPOSE OF STUDY:

The purpose of the present study is to continue clinical scanning on the NICU MRI with improved administrative processes and procedures, thereby making medically indicated, state of the art/high end MRI exams available to all infants treated at CCHMC.

BACKGROUND:

Complications related to prematurity and congenital malformations are the most common cause of morbidity in infants, and now contribute almost equally to infant mortality[1-4].

The diagnosis and management of many of these medical conditions commonly seen in the NICU could be improved by MR imaging. While MRI has been widely available to the adult patient population since the early 1980s, its use for premature and term infants has been extremely limited. Although some studies have shown the potential of MRI in these patients [5-9], routine clinical use remains beyond reach due to the potentially life-threatening risks associated with moving a baby out of the NICU for the exam. Although transporting neonates between departments is possible and has been successful in a few institutions [5, 10-16], the diagnostic image quality of neonatal MRI suffers considerably from the use of imaging technology optimized for adult anatomy [6-10, 17-29].

In order to address the need for neonatal access to high-end diagnostic MRI instrumentation, engineers and scientists in the Imaging Research Center (IRC) at CCHMC have adapted a commercially available, FDA cleared, small (21.8 cm diameter bore, as compared to 60-70 cm for a conventional scanner) 1.5T MRI system, the GE OPTIMA 430s, originally designed for adult orthopedic use. The operating manual and data sheets for this MRI system are included as Appendix A. The OPTIMA measurement control electronics and operating system software have been augmented with HDX/GE electronics and software (see Appendix B: HDX/GE platform operating manual and data sheets). The HDX/GE platform is FDA cleared and is used to operate much of the GE MRI product line, including scanners used clinically at CCHMC. The original OPTIMA electronics will remain operational with the OPTIMA hardware with the option to readily switch between the two operating platforms (i.e. HDX/GE vs. OPTIMA). This integration of the HDX/GE electronics and the OPTIMA hardware allows for advanced MR imaging more relevant to whole body and brain scanning.

An extensive detailed description of the modifications that were made to the systems to accommodate whole body MR imaging of the neonate and a detailed description of the patient table developed to accommodate the smaller size of the magnet are documented in the "BACKGROUND" section of CCHMC IRB Protocol 2011-2045 ("Pilot Study: Safety of a Customized MRI System for Neonatal Imaging") (See Appendix C: Detailed description of 1) modifications made to the MR systems to accommodate whole body MRI of the neonate; 2) patient table developed to accommodate the smaller size of the magnet).

PREVIOUS WORK IN THIS AREA:

Details of prior pre-clinical animal testing are documented in the "PREVIOUS WORK IN THIS AREA" section of CCHMC IRB Protocol 2011-2045 ("Pilot Study: Safety of a Customized MRI System for Neonatal Imaging"). (See Appendix D. Previous work done in this area on prototype neonatal MRI system). Further details about the NICU MRI system's safety testing are documented in the Previous Work In This Area section of protocol 2011-2045. The patient table, coils, specific absorption rate (SAR), acoustic noise, and peripheral nerve stimulation are all discussed. (See Appendix E: MR system safety testing data).

CCHMC IRB Protocol 2011-2045 was a pilot study including 15 neonates demonstrating safety and feasibility of the NICU MRI. Photographs from the scanning process and images from the first patients are attached in Appendix F. Permission to use the photographs was obtained from the parents of the baby.

Subsequently we have scanned nearly 600 patients on the NICU MRI without adverse event under CCHMC IRB Protocol 2011-2850.

STUDY METHODS:

This is a study to use a customized MRI system installed in the CCHMC NICU to perform medically indicated MRI exams in the neonatal population.

Study population:

Neonates admitted to CCHMC for whom an MRI exam is medically indicated will be recruited into the study. All neonates in the study will be viable, as defined in subpart B of the Code of Federal Regulations. The infants will be medically stable to undergo the MRI procedure, as determined by the attending neonatologist.

Study design:

Infants who may meet study criteria will be identified by the attending neonatologist and study staff will be notified of a potential candidate for the study. As per usual clinical care, orders for the MRI will be placed in EPIC.

Inclusion criteria:

- Any infant admitted to CCHMC
- Have a medical condition for which an MRI exam is indicated, as determined by the attending neonatologist

Exclusion criteria:

- Infants too large to fit in the customized NICU MRI system comfortably (generally infants > 6 kg)
- Standard MRI exclusion criteria as set forth by the CCHMC Division of Radiology

Pre-scan:

The attending neonatologist will determine whether the MRI scan is to be done with sedation or without sedation. Whenever possible, infants will be scanned without sedation utilizing a feed and bundle technique. Occasionally, at the discretion of the

neonatologist, sedation will be necessary to obtain the imaging required for clinical diagnosis. This mirrors the process utilized on the conventional magnets in the Department of Radiology. The use of sedation and/or contrast is not part of the research.

Prior to MRI scanning, the patient's NICU care team will attempt to contact parent/LAR to communicate that a MRI has been ordered and provide information on the device, any potential risks and answer any questions the parent/LAR may have.

Infants will be prepared for the MRI exam at the bedside by switching all monitoring devices over to MRI compatible monitors. Switching monitoring devices confers no additional risk to the patient. Hearing protection will be used for acoustic noise reduction. Infants will then be moved to the MRI control room and transferred to the patient table/transfer station by the NICU nurse and/or physician.

Standard MRI safety screening will be performed by the MRI technologist per Department of Radiology practice. Screening will be documented according to standard Department of Radiology procedure.

MRI scan:

All studies will be performed with a nurse and/or physician in the control room. The specific MR sequences used will be determined by the type of exam to be performed based on the medical indication. Some patients may get IV contrast and/or sedation if indicated by the specific MR exam protocol. The scanner will be operated by a certified MR technologist.

Sequences will be obtained using the OPTIMA electronics during each MRI exam in order to have images from a device that is FDA cleared. Additional sequences will be obtained with the HDX/GE platform. Images from the HDX/GE platform are expected to be of diagnostic quality equal to or better than those obtained from an adult-sized 1.5T MRI scanner. If the patient remains stable throughout the MRI exam, an additional 10 minutes of scanning beyond the clinically indicated sequences may be obtained for ongoing sequence development and improvement efforts.

All coils used will be FDA cleared. Those not cleared will be submitted to the IRB and approved before they are used.

Monitoring of safety and tolerability:

Adverse events will be monitored during the MRI scan by the MRI technologist and the nurse/physician in the control room. Only adverse events that take place during MRI scanning will be recorded. Adverse events will be recorded on an adverse event log form kept in the MRI control room. In the event of an adverse event, the study team will be notified and a full report of the specific event will be submitted to the IRB promptly. Nurses will collect vital signs for clinical care purposes, but there will be no vital sign collection as part of this protocol.

6

Evaluation of MRI data:

As is done for any medically indicated clinical MRI exam, all images acquired will be interpreted by a board certified pediatric radiologist or neuroradiologist and a standard report will be generated. This report will be included in the neonate's medical record and made available to the clinical team. The MRI data collected using the OPTIMA/HDX MRI platform will be used in conjunction with the images obtained using the FDA cleared OPTIMA MRI platform and the results of other appropriate standard diagnostic tests to inform diagnosis and/or subsequent medical management. Deidentified images may be used in publications or in support of a 510K application to the FDA.

Sample size:

The goal of this study is to make MRI available to all neonates admitted to CCHMC for whom an MRI exam is medically indicated. Thus, the maximum number of patients recruited into the study per year will reflect the maximum number of patients admitted into the NICU. A review of the historical data documenting the number of patients admitted to the CCHMC NICU over a five year period (2006 – 2010) indicated that on average, 714 (range 662-759) patients were admitted each year over that period.

DURATION:

This protocol is considered a continued access protocol and will remain open indefinitely.

POTENTIAL BENEFITS:

By eliminating the need to transfer neonates from the NICU to the main Radiology Department for an MRI exam, neonatal patients will benefit by avoiding the medical risk associated with removal from the NICU. Patients evaluated on the NICU MRI will also benefit from reduced acoustic noise, lower RF power deposition and less chance of peripheral nerve stimulation during the MR exam as compared to that associated with exams performed on the adult sized conventional MR scanner. Patients may also benefit from earlier and/or more comprehensive and accurate diagnosis and medical management.

POTENTIAL RISKS, DISCOMFORTS, AND INCONVENIENCES:

MRI exams are considered minimal risk for research purposes. The customized NICU MRI scanner will have no increase in risk beyond conventional adult MRI scanners. Although chart review is not part of this protocol, there is a risk of loss of confidentiality

of medical record information related to maintenance of research records. In order to protect the privacy of medical information, the research records will be coded and access to the records will be limited to research personnel. The MR report will be included in the clinical medical record to supplement diagnosis and medical management. All other study specific data (e.g. parental permission, safety record) will be de-identified and kept in a locked cabinet. No individual identifiers will be used in publications or reports resulting from the study. After the study is completed and the results are published, the records will be destroyed.

RISK/BENEFIT ANALYSIS:

In the opinion of the investigators, this study involves no increase over minimal risk with potential immediate and direct benefit to the study subjects and potential benefit to future patients and the scientific community. We believe that making MRI more readily available to this population will benefit their subsequent medical management. In addition, infants in the study may, in fact, have less risk than they would during an MRI scan obtained on a conventional clinical MRI system as part of usual clinical care, due to the decreased risk of acoustic noise injury and the elimination of the risk associated with transporting the infant out of the NICU to the Radiology department.

SECURITY/CONFIDENTIALITY:

All subjects enrolled in this study will be identified in research records by a unique study number only. The MR report will be included in the clinical medical record to supplement diagnosis and medical management. All other study specific data will be deidentified. Protected health information will be entered into a secure database. A single copy of a list linking medical record number to study number will be kept locked and available only to study investigators. All records will be kept in a locked cabinet at CCHMC and maintained by the study investigator. All computerized records will be password protected.

REIMBURSEMENT/PAYMENT FOR STUDIES:

The parents/LARs of the study patient and/or their medical insurance company will be responsible for the financial charges/costs associated with each of the MRI exams he/she receives using the OPTIMA NICU MRI platform while enrolled in the study as these are examinations being performed for clinical indications. These costs will be identical to those incurred by patients who receive MRI exams on the adult sized conventional MRI scanners in the main Radiology Department. The costs associated with additional imaging performed using the OPTIMA/HDX NICU MRI platform will be assumed by

the Department of Radiology. There will be no compensation or payment to the study participant.

RECRUITMENT:

Patients will be identified based on clinical need. After potential study subjects are identified, the NICU fellow or attending assigned to the patient (the fellow and attending are also part of the study team) will discuss the study with the parents/ LARs.

Informational flyers or materials directed at healthcare providers and/or the general public may be created. All marketing materials will be approved by the IRB prior to circulation.

CONSENT:

We are requesting a Waiver of Documentation of Informed Consent in accordance with 45 CFR 46.117 and 21CFR56.109 for this study. According to these regulations, the IRB may waive the requirements for investigators to obtain signed consent if one of two requirements are met. Our research study meets the second criterion that "the research presents no more than minimal risk of harm to subjects and involves no procedures for which written consent is normally required outside of the research context (45 CFR 46,117)".

MR imaging is of no more than minimal risk for patients and is performed daily for clinical care of children in the CCHMC system. Other than potential administration of intravenous contrast (utilized only when clinically indicated), there is no instrumentation of, or intervention on, the patient as part of the MRI exam. Accordingly, specific procedural consent is not signed by LARs for the performance of MRI on conventional scanners (or administration of intravenous contrast) as part of normal clinical care.

In regards to 45 CFR 164.501, 164.508, 164.512(i), all protected health information generated as part of this study will remain confidential in accordance with CCHMC best practices. PHI, including but not limited to, date of birth, name, medical history, must be used to safely and adequately perform and document an MR exam. PHI related to this clinical MR study will not be disclosed to any other person or entity for additional research without a specific study IRB. All images and patient data are maintained securely in CCHMC's protected clinical PACS and in EPIC, both of which have electronic access controls. Specifically, CCHMC personnel must request access to these systems from their manager and CCHMC Information Services. Granted access is dependent on their institutionally assigned job description and credentials. Clinical PACS and EPIC are highly secure systems, hosted and supervised by CCHMC network security and are HIPAA compliant.

Patient identifiers will be available to the patients' care team as part of their clinical duties. It is not possible for the study team to withhold the MR images generated as part of this study from the patient's clinical staff because they rely on them for diagnostic

9

purposes and withholding these images would deny these patients potential clinical benefit. At no point will we destroy patient identifiers as they are the patient's clinical identifiers.

In many cases the parent/LAR is not on site when the physician orders an MRI and NICU staff have to reach them by phone. Transferring NICU patients to the main Radiology Department has specific risks related to difficulties with mobile monitoring, inadequate environmental controls (for a population susceptible to heat loss) and exposure to a general hospital population. All parents/LARs of prospective patients will have the NICU MRI study explained to them by their clinical care team who order the MR scan- the nature of the scan, financial costs, and possible adverse reactions, none of which differ from conventional MRI scanners. It will be made clear that participation in the study is voluntary.

NICU fellows or attendings, who are part of the study staff, will use the study information sheet provided and the verbal script below to communicate and obtain consent from parents/LARs.

The fellow or attending taking care of patient will call the parents/LARs and introduces him/her self. The fellow or attending then verifies that they are speaking with the correct parent/LAR using information. The physician will tell the parent/LAR that their child is scheduled to have an MRI of their brain/spine/abdomen/etc. and explain why the MRI is needed. Next, they tell them that they are calling the get their permission to use our NICU MRI. The script that follows will be used after the above introduction:

"An MRI machine uses a computer and a big magnet to take pictures. The magnet in our NICU scanner is much smaller than the magnets used in the MRI machines downstairs in the Radiology department. We are one of the only NICU's in the country that have MRI capability within the NICU as opposed to the hospital-wide radiology suite. Our MRI machine uses a smaller magnet than a typical MRI machine. Individually the MRI magnet and imaging software are FDA approved, but together as one unit they are not, therefore, I need your permission to use our NICU MRI for your child's study. We use the same process for obtaining the study and are able to get the same quality images using this machine as we would if your child were to have their MRI done in radiology, but with the added benefit of not having to travel off the unit. There are no additional risks by using the NICU MRI and in general we find it safer and more seamless to obtain the images when not having to travel off the floor. The same Radiologists read these images and we are able to bill your baby's insurance. There are no additional costs beyond the costs of an MRI in the big scanner downstairs. We will collect basic information about your child and the type of scan that was performed as part of quality control for the study. There are no known risks to the MRI scan itself and the MRI does not involve radiation. If you do not wish to have your baby's MRI performed in the NICU, we will schedule your baby to move downstairs for the MRI- sometimes it takes a little longer to schedule that. Do you have any questions for me at this time? ... Do you consent to having your baby's scan being done in our custom- built NICU MRI?"

A participant information sheet will be provided to parents/LARs. This information sheet serves as a study summary.

Non-English speaking participants will be consented using an interpreter. The interpreter will read the verbal script above to the family. The NICU fellow or attending consenting the parent/LAR will be present to answer any questions and to confirm the family understands the research. A witness (any available NICU staff) will be present to confirm the process has been completed. The fellow or attending will document consent has been obtained and that all questions have been answered, in addition to, the interpreter's name, ID, and credentials and the witness' name and credentials in the EPIC process note. This note will also be saved into the patient's research record.

This instance is rare. Under CCHMC IRB 2011-2850 we obtained consent from two non-English speaking parents/LARs on average per year. This is in comparison to the 110 English speaking parents/LARs on average per year.

DATA SAFETY AND MONITORING PLAN:

As the study involves no increase over minimal risk, no Data Safety Monitoring Board will be created for this study. The study PI will communicate regularly with the study coordinator and will review documentation and any AEs that have occurred.

All unanticipated problems and adverse event will be submitted to the IRB per institutional policy.

CONCURRENT RESEARCH PROTOCOLS:

Subjects will be allowed to participate in other research protocol(s) concurrently.

APPENDICES:

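### Does an inclusion criterion worded for the whole hospital admit infants whom the NICU-based procedures do not cover?

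*Protocol*

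**What the plan says.** The Protocol describes its population in wide terms in some places and narrow terms in others.

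- **Wide.** Purpose of Study aims to make "state of the art/high end MRI exams available to all infants treated at CCHMC". Study population says "Neonates admitted to CCHMC for whom an MRI exam is medically indicated will be recruited into the study". The first inclusion criterion is "Any infant admitted to CCHMC". The opening sentence of Sample size also speaks of neonates admitted to the hospital, without naming the NICU.
- **Narrow.** The Abstract says "NICU patients for whom an MRI exam is medically indicated will be recruited for the present study". Sample size goes on to say that "the maximum number of patients recruited into the study per year will reflect the maximum number of patients admitted into the NICU". Recruitment has the study discussed with parents by "the NICU fellow or attending assigned to the patient". Potential Benefits states that "neonatal patients will benefit by avoiding the medical risk associated with removal from the NICU", and Risk/Benefit Analysis cites "the elimination of the risk associated with transporting the infant out of the NICU to the Radiology department".

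Two further eligibility rules limit the wide wording. The attending neonatologist must judge that an MRI is indicated, and infants too large for the bore (generally above 6 kg) are excluded. No age limit is given.

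**The concern.** Eligibility belongs in the protocol and cannot be left to an analysis plan, so an unclear criterion deserves attention. Take an infant on another ward, small enough for the scanner, whose MRI a neonatologist supports. That infant meets the inclusion criteria but is not among the patients whom the Abstract recruits.

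Three later statements would then fail:

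- The consent script presents staying on the unit as an advantage, yet this infant would have to leave its own ward to reach the scanner.
- The transport part of the risk/benefit case would not apply.
- NICU admissions would no longer be an upper bound on yearly recruitment.

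The script matters more than usual here, because the Protocol asks for a waiver of signed consent. Parents rely on the spoken script and an information sheet. The Protocol is also open-ended, so the ambiguity would not lapse with the end of recruitment.

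**Working it through.** **1. The stated figure.** Sample size gives a mean of 714 NICU admissions a year (range 662 to 759) over 2006 to 2010. This is a historical count, not a power calculation. The yearly counts are not given, so the mean cannot be recomputed, but it can be checked against the range. The five-year total is 5 × 714 = 3570. Removing the lowest and highest years leaves 3570 − 662 − 759 = 2149 over three years, or 2149 / 3 ≈ 716 a year. This lies inside the range, so mean and range are compatible.

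**2. Does the ceiling come under strain?** Consent reports average yearly consents under the preceding protocol (2011-2850): 110 from English-speaking and 2 from non-English-speaking parents or representatives.

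- Total: 110 + 2 = 112 a year
- Against the mean year: 112 / 714 = 15.7%
- Against the highest year: 112 / 759 = 14.8%

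If uptake is similar and each consent covers one infant, recruitment is far below the ceiling. A few infants from elsewhere would not bring it near.

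**3. Can a ward infant reach the scanner under the text?** The steps, in order:

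| Step | Section | Who or where |
|---|---|---|
| Study location | Title page | The hospital's NICU |
| Candidate identified | Study design | Attending neonatologist |
| Indication judged | Inclusion criteria | Attending neonatologist |
| Parents contacted | Pre-scan | The patient's NICU care team |
| Infant moved and transferred to the table | Pre-scan | NICU nurse and/or physician |
| Study discussed | Recruitment | "the NICU fellow or attending assigned to the patient" |
| Consent obtained | Consent | NICU fellows or attendings on the study staff |

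Each step presupposes NICU care or a neonatologist's decision. No section gives another route for identification, consent or transfer.

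**4. How the Protocol uses its own wide term.** Sample size states its goal for neonates admitted to the hospital and, as a direct consequence, sets the maximum by NICU admissions. That inference holds only if the two groups are taken to be the same. The sensible reading is that the authors use hospital admission, for this population, to mean NICU admission. On that reading the ceiling, the script and the transport argument are all consistent.

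**5. Number of families affected.** The Protocol gives no count of eligible infants outside the NICU. Any assumed share of the 112 would lack support and could be zero. The eligibility rules of the preceding protocol are not shown either. No figure can be defended.

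**The case for a change.** The best case for a change is that the wide wording is not one stray bullet. It appears in the purpose, the study population, the inclusion criterion and the sample-size goal. The neonatologist's role concerns the indication for MRI and is not an admission requirement, and the Protocol never says that neonatologists attend only in the NICU. If a ward infant were scanned, the script would mislead the parents on transport. Events on the way to the NICU would also go unrecorded, because only adverse events during scanning are logged. Aligning a few sentences costs almost nothing.

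The textual part of this stands: the sections do not match, and the formal criterion is wider than the procedures. The consequences do not follow. Parents hear the script from a NICU physician assigned to their child, so an infant with no such physician would not reach it. The benefit case does not rest on transport alone: Potential Benefits also lists less noise, lower radiofrequency deposition and less nerve stimulation, which apply to any infant scanned. Possible use of de-identified images in publications or a device application carries no stated claim about the population, so it adds little. An age limit is not needed to make the text workable, since Study methods uses neonate and infant interchangeably and the size limit is the one that matters for this scanner. A second consent script would serve a pathway that the Protocol does not describe.

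**Conclusion.** The inconsistency is real but editorial, and no change to the plan follows. The wide phrases in Purpose of Study, Study population and Inclusion criteria are narrowed by every operating step. A reader applying the whole Protocol would enrol NICU patients under either wording. No endpoint, figure or safety procedure would differ, and the yearly ceiling stays remote at about 112 consents against 714 to 759 admissions.

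This rests on two assumptions. The first is that NICU fellows and attendings are assigned to NICU patients, which the text implies but does not state. The second is that uptake resembles that under the preceding protocol, with one infant per consent. Nothing in the Protocol shows that an infant outside the NICU has been or would be enrolled. The phrases could be brought into line when the document is next revised, but that would be housekeeping and would not alter whom the study enrols or what it can conclude.

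### Does the expectation that HDX images match an adult-sized 1.5T scanner oblige the protocol to rate the HDX and OPTIMA images separately?

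*Protocol*

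**What the plan says.** Under STUDY METHODS, MRI scan, the protocol gives two roles to the two platforms. On OPTIMA: "Sequences will be obtained using the OPTIMA electronics during each MRI exam in order to have images from a device that is FDA cleared". HDX sequences are then added, with the remark that their images are "expected to be of diagnostic quality equal to or better than those obtained from an adult-sized 1.5T MRI scanner".

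Under Evaluation of MRI data, a pediatric radiologist or neuroradiologist interprets everything acquired and issues a standard report. The HDX data "will be used in conjunction with the images obtained using the FDA cleared OPTIMA MRI platform" and other diagnostic tests to inform care. The same section adds: "Deidentified images may be used in publications or in support of a 510K application to the FDA".

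The verbal script under CONSENT goes further than the methods. It tells parents that staff are "able to get the same quality images using this machine" as they would in Radiology.

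The aim is given under PURPOSE OF STUDY: "The purpose of the present study is to continue clinical scanning on the NICU MRI with improved administrative processes and procedures". Under DURATION: "This protocol is considered a continued access protocol and will remain open indefinitely". The Sample size section gives a yearly ceiling based on past NICU admissions and no power calculation. The ABSTRACT cites diagnostic image quality in 15 pilot patients, and cites almost 600 later patients for the absence of adverse events.

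**The concern.** The statement names an adult-sized 1.5T scanner as its reference, yet no enrolled infant is planned to be imaged on one. In the script, that scanner is the route for families who decline. Each exam does yield images from both NICU platforms in the same infant, which looks like a natural paired comparison, but no quality score is described for either. On this reading the protocol could run for years, at about 112 infants a year, without learning whether HDX images are diagnostic on their own or better than OPTIMA images.

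Three things would be at stake. Parents hear equality stated as fact. Images could later go into a 510K application or a publication without having been rated, and with room to choose the best. And the evidence cited for image quality is small.

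**Working it through.** **1. Is there a figure to reproduce?** No. The protocol states no image-quality endpoint, margin, alpha, power or powered sample size. The only sample-size figure is the historical average of 714 admissions a year (range 662 to 759), which serves as an accrual ceiling.

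**2. How strong is the cited evidence?** Assume all 15 pilot infants had diagnostic images; the protocol does not give the count. The exact two-sided 95% lower limit is 0.025^(1/15) = 0.782, and the one-sided limit is 0.05^(1/15) = 0.819. The sample is indeed small. But this limit describes the proportion of exams that are diagnostic. It measures neither HDX against an adult-sized scanner nor HDX against OPTIMA.

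**3. What would a real comparison need?** For illustration only, take one-sided alpha 0.025, power 80% and no true difference. Accrual under the prior protocol was 110 + 2 = 112 families a year (CONSENT section). All margins, discordance rates and diagnostic rates below are assumptions.

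Paired non-inferiority: n = (1.960 + 0.842)² × discordance / margin², where the squared term is 7.849.

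| Margin | Discordance 10% | Discordance 30% | Years at 112 a year |
|---|---|---|---|
| 10 points | 7.849 × 0.10 / 0.01 = 79 | 7.849 × 0.30 / 0.01 = 236 | 0.7 to 2.1 |
| 5 points | 7.849 × 0.10 / 0.0025 = 314 | 7.849 × 0.30 / 0.0025 = 942 | 2.8 to 8.4 |

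Unpaired comparison with a conventional-scanner group: n per group = 7.849 × 2p(1 − p) / margin².

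| Margin | p = 95% | p = 85% |
|---|---|---|
| 10 points | 75 | 201 |
| 5 points | 299 | 801 |

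The paired design is feasible at this accrual. However, it applies only to HDX versus OPTIMA. The adult-scanner statement would need the second design, with a group of infants that this protocol does not enrol.

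**4. Is the OPTIMA/HDX pair like for like?** The text does not support that. HDX sequences are described as additional to the OPTIMA ones. BACKGROUND explains that the HDX electronics were added to allow more advanced imaging, and nowhere is the same sequence said to be run on both platforms. OPTIMA images are taken so that images from a cleared device exist, which is a regulatory reason and not a comparator role. A paired score difference would mix platform with sequence type.

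**5. Does the statement act as a study claim?** Set beside PURPOSE OF STUDY and DURATION, it does not. The aim is access and improved administration. Data collection is kept thin on purpose: the protocol excludes vital-sign collection and chart review. No planned analysis uses the expectation as an input or reports on it.

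**The case for a change.** The strongest opposing case is that a later analysis plan cannot recover ratings that nobody recorded, and that the protocol looks beyond access. It foresees publications and possible 510K support, refers to the results being published, and allows ten extra minutes of scanning for sequence development. Image quality is central to its rationale. Two short fields per read would cost little, and one year at about 112 infants would far exceed the 15 pilot infants.

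Part of this stands. The data as described cannot support a claim of equality with an adult-sized scanner, and the script states as settled what the methods only expect.

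The rest does not carry a change. Images remain in the clinical archive, so consecutive exams could still be read later, with blinding, if someone takes up that question. Using the two image sets together for diagnosis does not bar such a reading. Ratings by an unblinded clinical reader on unmatched sequences would be weak support for a regulatory filing. The 510K sentence says only that images may be used; it promises no performance estimate, so harm from selective choice is conjecture. If the adult-scanner wording were softened, the main reason for the rating scheme would largely go with it. The scheme would then be a new study aim, on which reasonable statisticians would differ.

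**Conclusion.** The factual observations are right: there is no adult-scanner arm, one standard report per exam, and no per-platform rating described. They do not amount to a design fault. The protocol sets no image-quality objective, and the proposed pairing could not answer the question the sentence raises. The 78% limit is correct arithmetic on an assumed 15 out of 15, but it measures a different quantity.

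What survives is a clerical mismatch in strength between the MRI scan section and the verbal script. Aligning the two would be a matter of consent wording and would alter no result, estimate or conclusion. Analysts and authors can meet the rest by making no equality or superiority claim from these data.

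This rests on two conditions: that the purpose remains continued access as stated, and that no image-quality endpoint is set in a document not shown here. If the team later wished to claim comparative quality, it would need its own protocol with matched sequences, blinded reading and a conventional-scanner group.
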